## 10 ADVERSE EVENT DEFINITIONS / PHARMACOVIGILANCE

#### 10.1 Terms and Definitions

#### **Adverse Event (AE)**

Any untoward medical occurrence in a patient or clinical research subject which does not necessarily have a causal relationship with an investigational procedure or the medicinal product.

#### Adverse Reaction (AR)

Any untoward and unintended response in a subject which, in the opinion of the investigator, is related to the medicinal product or to an investigational procedure.

#### **Unexpected Adverse Reaction (UAR)**

An adverse reaction the nature and severity of which is not consistent with the information about the investigational procedure or medicinal product in question set out in: In the case of a product with a marketing authorisation, in the summary of product characteristics for that product.

## Serious Adverse Event (SAE), Serious Adverse Reaction (SAR) or Suspected Unexpected Serious Adverse Reaction (SUSAR)

Any adverse event, adverse reaction or unexpected adverse reaction, respectively, that:

- results in death
- is life-threatening\* (subject at immediate risk of death)
- requires in-patient hospitalisation or prolongation of existing hospitalisation\*\*
- · results in persistent or significant disability or incapacity, or
- consists of a congenital anomaly or birth defect
- Other important medical events\*\*\*
- \*'life-threatening' in the definition of 'serious' refers to an event in which the patient was at risk of death at the time of the event; it does not refer to an event which hypothetically might have caused death if it were more severe.
- \*\*Hospitalisation is defined as an inpatient admission, regardless of length of stay, even if the hospitalisation is a precautionary measure for continued observation. Hospitalisations for a pre-existing condition, including elective procedures that have not worsened, do not constitute an SAE.
- \*\*\*Other important medical events that may not result in death, be life-threatening, or require hospitalisation may be considered a serious adverse event/experience when, based upon appropriate medical judgment, they may jeopardise the subject and may require medical or surgical intervention to prevent one of the outcomes listed in this definition

#### Suspected Unexpected Serious Adverse Reaction (SUSAR)

An SAE occurring to a research participant where in the opinion of the Investigator the event was:

a. **related**: resulted from the administration of any of the research procedures or the medicinal product, and b. **unexpected**: the type of event is not listed in the protocol or SmPC as an expected occurrence.

#### 10.2 Notes on adverse event inclusions and exclusions

#### **10.2.1** Include

An exacerbation of a pre-existing illness

- An increase in frequency or intensity of a pre-existing episodic event/condition.
- A condition (even though it may have been present prior to the start of the study) detected after study drug administration.
- Continuous persistent disease or symptoms present at baseline that worsens following the administration of the study treatment.
- Laboratory abnormalities that require clinical intervention or further investigation (unless they are associated with an already reported clinical event).
- Abnormalities in physiological testing or physical examination that require further investigation or clinical intervention.
- Injury or accidents.

#### 10.2.2 Do not include

- Medical or surgical procedures the condition which leads to the procedure is the adverse event.
- Pre-existing disease or conditions present before treatment that do not worsen.
- Situations where an untoward medical occurrence has occurred e.g. cosmetic elective surgery.
- Overdose of medication without signs or symptoms.
- The disease being treated or associated symptoms/signs unless more severe than expected for the patient's condition.

#### 10.2.3 Reporting of pregnancy

Females of childbearing potential will be tested for pregnancy as per local clinical protocol. Any pregnancy that occurs will be reported, and it is the local PIs responsibility to discuss the need for cessation of the systemic medicine with the patient. All pregnancies that occur during treatment need to be followed up, until after the outcome. Verbal consent to report information regarding these pregnancy outcomes should be obtained from the mother and recorded in the medical notes.

Any pregnancies that results in complication will be reported to the MHRA (UK sites) or HPRA (Irish sites) by the patient's treating physician.

## 10.3 Notes severity / grading of adverse events

The assignment of the severity/grading should be made by the local investigator responsible for the care of the participant using the definitions below.

Regardless of the classification of an AE as serious or not, its severity must be assessed according to medical criteria alone using the following categories:

**Mild**: does not interfere with routine activities **Moderate**: interferes with routine activities **Severe**: impossible to perform routine activities

A distinction is drawn between serious and severe AEs. Severity is a measure of intensity (see above) whereas seriousness is defined using the criteria in section 10.1, hence, a severe AE need not necessarily be a Serious Adverse Event.

## 10.4 Causality

The assignment of the causality should be made by the investigator responsible for the care of the participant using the definitions in table 2.

**Table 2: Definitions of causality** 

Relationship	Description	
Unlikely	There is none or little evidence to suggest there is a causal relationship	
	(e.g. the event did not occur within a reasonable time after	
	administration of the medication or study procedure). There is another	
	reasonable explanation for the event (e.g. the participant's clinical	
	condition, other concomitant treatment).	
Likely	There is some evidence to suggest a causal relationship (e.g. because	
	the event occurs within a reasonable time after administration of the	
	medication or study procedure). However, the influence of other	
	factors may have contributed to the event (e.g. the participant's clinical	
	condition, other concomitant treatments).	
Confirmed	There is clear evidence to suggest a causal relationship and other	
	possible contributing factors can be ruled out.	

## 10.5 Expectedness

An AE whose causal relationship to the study drug or study procedure is assessed by the investigator as "likely" or "confirmed" is an Adverse Drug Reaction.

All events judged by the investigator to be "likely" or "confirmed" related to the therapy or study procedure, graded as serious and **unexpected** should be reported as a SUSAR.

Expected reactions to study procedures are:

- Blood testing: temporary discomfort from the needled in the arm, bleeding, bruising, swelling at the needle site, infection.
- Skin biopsy: bleeding, discomfort, infection, scarring, hyperpigmentation, intolerance reactions to local anaesthetic.
- Tape stripping: mild discomfort

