#### Adverse events/pharmacovigilance:

Drug adverse events are calculated per person time of follow up, after the start of therapy. Time-dependent regression analyses will be undertaken to compare event rates between groups, using standard multivariable analyses to reduce confounding. We will explore the use of other statistical techniques, including propensity score matching, to accommodate confounding by indication. As children and adolescents may have a different phenotype of atopic eczema compared to adults and may respond differently to systemic therapy, we will explore this further in comparative analyses.

Estimating the risk of rare adverse effects with a smaller signal, especially lymphoma will be facilitated by long-term linkage to the national cancer registry (in addition to the control group). The risk window for cancer being defined as once exposed always at risk. Where two biologicals have been used, the proportion of time spent on each will define its possible contribution to risk. Where the adverse event is rare or where a biological intervention is under-represented in the register, the numbers of patient's data can also potentially be increased by sharing data with other compatible registers such as those operating in Germany, Italy, Spain, France, Denmark, and the Netherlands.

The aim in the long-term is to recruit at least 4,000 patients on conventional treatments and also at least 2,000 on each biological intervention (depending on the uptake of these drugs in clinical practice). 4,000 patients in

each cohort, biologicals and conventional treatment would give an exposure of 12,000 patient years in each group. This would give power to detect at least a 3- or 4-fold increase in risk of events occurring at a frequency of 1 in a 1000 or 1 in 2000 patients. Rarer events would be detected if the relative risks were higher.

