### 10.9.1 Safety reports

Safety reports will be generated during the course of the study, which allows for monitoring of SAE and AR reporting rates across sites and drug groups. The Study Co-ordinating Centre will generate pre-defined sixmonthly safety update reports containing a list of all adverse events.

Any concerns raised by the SSC or the SMG or inconsistencies noted at a given site may prompt additional training at sites.

Additional training will also be provided if unacceptable delay in safety reporting timelines occurs. If any safety reports identify issues that have implications for the safety of study participants, the PIs at all institutions participating in the study will be notified.

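### Section 10.5 labels procedure-related events Adverse Drug Reactions, and nothing removes them from the AR class monitored by drug group and reported to the regulator

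*Protocol*

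**What the plan says.** Section 10.5 turns the causality grade into a class of event: "AE whose causal relationship to the study drug or study procedure is assessed by the investigator as 'likely' or 'confirmed' is an Adverse Drug Reaction". Section 10.1 defines an Adverse Reaction as a response that, in the investigator's opinion, "is related to the medicinal product or to an investigational procedure". The SUSAR definition in 10.1 pools in the same way: related means that the event "resulted from the administration of any of the research procedures or the medicinal product". Table 2 has a single three-level scale whose descriptions refer to medication and study procedure together.

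The class is used in two places. Section 10.9.1 describes safety reports, "which allows for monitoring of SAE and AR reporting rates across sites and drug groups". Table 3 has one row for drug-related SARs and another for ARs for medicines under additional monitoring; both go to the MHRA or HPRA.

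Other text bears on the separation. Section 8.2 asks in the adverse event history whether the event may be related to the patient's systemic therapy, with no mention of procedures. Section 10.5 lists expected procedure reactions apart from those for medicinal products, which it refers to the SmPC. Section 9.4 says: "Drug adverse events are calculated per person time of follow up, after the start of therapy".

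**The concern.** A reaction to a biopsy or a research blood draw says nothing about the safety of the medicine the patient takes. If the definition places it in the same class as drug reactions, an AR rate by drug group or by site partly reflects who was sampled.

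Sampling is not spread evenly. Biopsies and tape strips are optional and taken only at some sites, and biopsies are limited to patients aged 16 or over (8.3.3). Drug-level samples depend on the therapy prescribed, with methotrexate and biologics named.

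Infection is the most awkward overlap. Section 10.5 lists it as an expected reaction to blood testing and to biopsy, while 8.2 prompts for serious infection, including of skin and soft tissue, as a safety event. Under the literal wording, a procedural reaction in a patient on a medicine under additional monitoring would also fall in the row sent to the regulator as a reaction to that medicine.

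**Working it through.** The protocol gives no figure on this point, so there is none to reproduce. The check is a reading of the definitions against the places that use them.

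| Place | Cause covered | Drug and procedure separated? |
|---|---|---|
| 10.1, AR | medicine or procedure | no |
| 10.1, SUSAR, related | medicine or procedure | no |
| Table 2, causality grade | medicine or procedure, one scale | no |
| 10.5, Adverse Drug Reaction | medicine or procedure | no, and the label says drug |
| 10.5, expected reactions | two lists | yes, for expectedness only |
| 8.2, relatedness prompt | systemic therapy only | yes, but not linked to the AR class |
| 10.7.2, serious events | causality listed as one item | does not say causality to what |
| 10.9.1, AR rates | AR, by site and drug group | no exclusion stated |
| Table 3, SAR row | drug-related | yes |
| Table 3, additional-monitoring row | AR | no qualifier |

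1. Take a biopsy-site infection after the start of treatment that the investigator attributes entirely to the biopsy. Under Table 2 it can be graded likely or confirmed, because a study procedure suffices.
2. Under 10.5 it is then an Adverse Drug Reaction. Under 10.1 it is an AR.
3. Under 10.9.1 it belongs to the class whose rate is monitored for the patient's drug group. No sentence excludes it.
4. If the medicine is under additional monitoring, the Table 3 row read with the 10.1 definition includes it. The SAR row shows that a drug-related limit was available, and it was not carried across.
5. Could other text take the event out again? The 8.2 prompt asks about a reasonable possibility, whereas 10.5 builds the reaction on the Table 2 grade, and no passage says that the 8.2 answer decides what is an AR. The list introduced by "Expected reactions to study procedures are" settles whether an event is expected, not which cause it had. The drug-related limit in Table 3 covers serious reactions only, whereas bruising, discomfort and minor infection would usually be non-serious.

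Timing narrows the exposure. The schedule places skin sampling at baseline, V2 and V3. Baseline normally precedes the start of therapy, and 10.7 records adverse events from initiation of treatment. Reactions to baseline biopsies therefore mostly fall outside, leaving the V2 and V3 samples.

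**The case against.** The strongest reply is that this is a slip of wording with no shown effect. Much of that reply stands.

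- No passage says that procedural reactions are charged to the patient's drug. A reader might infer that they are counted that way in practice. The documents support only that the definition puts them in the class and that nothing removes them.
- The 8.2 item on relation to therapy, together with MedDRA coding of events, makes separation possible. The eCRF is not available to check. This shows that the data may exist, not that the AR rates use them.
- A reader might infer that the comparative safety results are biased. The term Adverse Drug Reaction appears only in 10.5. The safety endpoint in 9.2 and the analysis in 9.4 speak of drug adverse events and do not refer to 10.5 or to the AR class. Section 10.9.1 is surveillance, where a site inconsistency may prompt training. The stronger reading is not supported.
- A reader might infer that all such reactions are confined to bioresource participants at selected sites. That is wrong for blood draws: safety bloods are recommended at all study visits, and every centre may take the genetic sample. The restriction to selected sites applies to biopsies, tape strips and similar samples.
- Both regulator rows use channels meant for medicine reactions, so a sensible investigator would probably not submit a bruise. That relies on judgement against the literal wording, and the missing limit in one of two neighbouring rows remains.

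**Conclusion.** The point holds as a misclassification risk created by the definitions. Sections 10.1 and 10.5 and Table 2 pool drug and procedure causes. The pooled class is what 10.9.1 monitors by drug group and what one row of Table 3 sends to the regulator, and no text excludes procedure-related events from either use.

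The size cannot be stated. The protocol gives neither bioresource uptake by drug nor reaction rates for the procedures, so any figure would rest on invented inputs. It is probably limited: the skin procedures are optional, biopsies are restricted by age, and baseline sampling mostly precedes adverse event recording.

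The effect is on AR rates in the safety reports and on additional-monitoring submissions. An effect on the 9.2 and 9.4 comparisons is not demonstrated. The conclusion assumes that AR in 10.9.1 and Table 3 carries its 10.1 definition, which is the only definition of AR that the protocol gives.

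**What to change.** - In 10.5, reserve Adverse Drug Reaction for events graded likely or confirmed in relation to the medicine. Define procedure-related reaction as a separate term, and align 10.1 with it.
- Apply the Table 2 grade twice, once for the medicine and once for the research procedure. The therapy-relatedness item in 8.2 is the natural starting point for the first.
- State in 10.9.1 that AR rates by drug group use medicine-related events only, and tabulate procedure-related reactions by procedure.
- State in Table 3 that the additional-monitoring row refers to medicine-related ARs, to match the limit in the SAR row.

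The cost is a few lines of wording and at most one further eCRF field. No change to visits or sampling is needed.

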#### **Expected reactions to medicinal products**

For further details or latest up-to-date list of events consult the latest SmPC.

## 10.6 Follow-up after adverse events

All adverse events should be followed until satisfactory resolution or until the investigator responsible for the care of the participant deems the event to be chronic or the patient to be stable.

The investigator responsible for the care of the participant should apply the following criteria to provide information relating to event outcomes: resolved; resolved with sequelae (specifying with additional narrative); not resolved/ongoing; ongoing at final follow-up; fatal or unknown.

# 10.7 Reporting procedures

All adverse events should be recorded from initiation of treatment until withdrawn from study. Depending on the nature of the event the reporting procedures below should be followed. Any questions concerning adverse

#### A-STAR Protocol V5.0 (08-APR-2025) - IRAS Number: 237309

event reporting should be directed to the Study Co-ordinating Centre in the first instance. A table is given below to aid in determining reporting requirements.

### 10.7.1 Non-serious ARs/AEs

All such events, whether expected or not, should be recorded as Adverse Event on the eCRF.

### 10.7.2 Serious ARs/AEs/SUSARs

SARs, SAEs and SUSARs should be recorded on the eCRF. The eCRF form asks for the nature of event, date of onset, severity, outcome and causality.

All investigators will be informed of all SUSARs occurring throughout the study. Local investigators should additionally report any SUSARs and /or SAEs as required locally.

Reporting of AEs will be done according to table 3.

## 10.8 Responsibilities – Investigator

The Investigator is responsible for reporting all AEs in the eCRF that are observed or reported during the study, regardless of their relationship to study product. The participating investigators should share results of supplementary investigations into the adverse event (e.g. autopsy reports, admission records).

Patient safety incidents that take place in the course of research should be reported to the National Patient Safety Agency (NPSA) by each participating NHS/Irish Health Service Trust in accordance with local reporting procedures.

# 10.9 Responsibilities - Study Co-ordinating Centre

The Study Co-ordinating Centre will review adverse event data completeness and plausibility, and will query with the site any missing or inconsistent data.

The SCC will then produce safety reports for the different Committees and study partners, as per relevant agreements.

### 10.9.1 Safety reports

Safety reports will be generated during the course of the study, which allows for monitoring of SAE and AR reporting rates across sites and drug groups. The Study Co-ordinating Centre will generate pre-defined sixmonthly safety update reports containing a list of all adverse events.

Any concerns raised by the SSC or the SMG or inconsistencies noted at a given site may prompt additional training at sites.

Additional training will also be provided if unacceptable delay in safety reporting timelines occurs. If any safety reports identify issues that have implications for the safety of study participants, the PIs at all institutions participating in the study will be notified.

**Table 3: Safety reporting responsibilities for Principal Investigators** 

Event	When	How	To Whom
All AEs	Within 21 days	Via electronic CRF	Study co-ordinating
			centre
Drug-related	Within 21 days	Electronic submission through:	MHRA (UK) or HPRA
SAR		-Yellow card scheme for UK sites	(Ireland).
		https://yellowcard.mhra.gov.uk/	
		-HPRA website for Irish sites	Study co-ordinating
		https://www.hpra.ie/homepage/about-us/report-	centre
		an-issue (Human Medicine Adverse Reaction)	
		-Study co-ordinating centre: eCRF	
AR for	Within 21 days	Electronic submission through:	MHRA (UK) and HPRA
Medicines		-Yellow card scheme for UK sites	(Ireland).
under		https://yellowcard.mhra.gov.uk/yellowcards/report	
additional		mediator/	Study Co-ordinating
monitoring a		-HPRA website for Irish sites	Centre
		https://www.hpra.ie/homepage/about-us/report-	
		an-issue (Human Medicine Adverse Reaction)	
		-Study Co-ordinating Centre: eCRF	

a. Medicines under additional monitoring are those who display an inverted Black Triangle V in the SmPC. The black triangle symbol identifies newly licensed medicines that require additional monitoring by the EMA. Such medicines include new active substances, biosimilar medicines, and medicines that the EMA consider require additional monitoring. The latest list can be found in: www.mhra.gov.uk/blacktriangle or EMA website.

### 11 ETHICAL CONSIDERATIONS

### 11.1 Ethical Considerations

The study will abide by the principles of the World Medical Association Declaration of Helsinki (2013 amendment) and the principles of GCP and in accordance with all applicable regulatory requirements. This protocol and related documents will be submitted for review to HRA and NRES.

There are no major ethical issues with this study, as it is observational in nature. However, the following points have been considered:

- Medications under observation: Whilst all drugs studied have potential side effects, in particular the conventional immuno-suppressive agents, they are used in standard clinical practice. Full information about possible risks and benefits of all medications will be provided to parents and participants and data on adverse events will be collected and monitored throughout the study. In addition, the treatment of severe atopic eczema in participants will not be compromised by participation in the study. The precise risks and benefits of participating in the study will be outlined in patient information sheets, to be formulated with service user involvement.
- Blood testing: The risks of taking blood include temporary discomfort from the needle in the arm, bleeding, bruising, swelling at the needle site and, in rare instances, infection.
- Other tests for those who consent to the participation in the biorepository module (patients can individually opt into these investigations):
- Skin biopsy: skin sample from lesional and non-lesional skin at baseline, V2 and V3. Every biopsy carries the risk of bleeding, discomfort, infection and scarring, and separate consent will be taken for this procedure. Local anaesthetic will be used to numb the skin beforehand, and intolerance reactions might occur but are very rare.
- Tape stripping: this involves several applications of a sticky disc (like Sellotape) to the skin and is not uncomfortable.
- Skin microbiome: taking skin microbiome samples (ideally the area immediately adjacent to and just before the biopsy, if taken). The sampling procedure is non-invasive and easy to perform, similar to taking a conventional skin swab for bacterial culture.
- Consent in paediatric population: Children up to the age of 16 will be eligible for enrolment in the study and age-appropriate Participant Information Sheets (PISs) will be prepared in line with current guidelines. See section 11.2 for further details.
- Questionnaires: Participants will be asked to complete a number of questionnaires, some of them
  which could be upsetting or considered burdensome. Patient will be informed that they can omit
  questions. Patients can also withdraw their consent to complete further questionnaires at any time.

